HYPOTHESIS 1: BDD subjects will be differentiated from UD and HC subjects on measures of resting state corticoamygdalar connectivity and task-induced activation: BDD subjects will have lower lateral orbitofrontal (LOFC)-amygdalar connectivity but higher ventral anterior cingulate cortex (vACC)-amygdalar connectivity compared to UD and HC subjects. On measures of activation, while performing a happy emotion NoGo-Go task, UD subjects will have less dorsal ACC (dACC) activation compared to BDD and HC subjects.

SPECIFIC AIM 2: To investigate similarities and differences between BDD, HRUD and LRUD on measures of corticoamygdalar connectivity and activation.

HYPOTHESIS 2: HRUD subjects will display a pattern of corticoamygdalar connectivity and task-induced activation which will have similarities and differences with both BDD and LRUD subjects: HRUD subjects will have lower LOFC-amygdalar connectivity similar to BDD subjects but also lower vACC-amygdalar connectivity similar to LRUD subjects. On measures of activation, on the happy emotion NoGo-Go task, HRUD and LRUD subjects would have a similarly decreased dACC activation but on a negative facial emotion recognition task both HRUD and BDD will have lower insula activation compared to LRUD subjects.

EXPLORATORY AIM 3: Ultimately, only prospective data regarding which patients actually develop BD can validate the ability of the baseline imaging measures to predict a BDD or UD diagnosis. The main indicator of bipolarity is the presence of hypo(manic) symptoms. Beside conversion to (hypo)mania we will also measure occurrence of episodes of sub-threshold hypomania symptoms using the Young Mania rating Scale (YMRS) and the mania syndrome checklist of the Schedule for Depression and Schizophrenia (MSC-SADS) which has been recently used to study hypomania development in depressed patients. Besides looking at differences between converters and non-converters, an analysis will also be conducted of the correlation between peak change of YMRS and MSC-SADS scores as well as the slope of the change for mania symptoms ratings obtained over the course of the two years of follow-up. The data could be used to plan future large scale definitive studies.

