connectivity besides the use of conventional fMRI regional activation paradigms of response to emotional stimuli. Preliminary findings (described below) from our studies support this hypothesis and provide rationale to conduct a definitive clinically relevant study.

2cii. Methods and Design:

We plan to recruit unmedicated 40 BDD, 60 HRUD, 60 LRUD as well as 40 HC subjects closely matched for age, gender and ethnicity for the study. We expect that at baseline 10% of subjects could be lost. During follow-up 15 - 20 % of HRUD and LRUD of patients may be lost before adequate data for development of (hypo)mania is collected. The number of subjects remaining will be adequate for statistical analysis proposed. For the exploratory aim, both the UD groups will be offered 24 months of antidepressant treatment with frequent mood assessments in the study. The other BDD and HC subjects will be followed up by phone for 24 months. During the 24 months all subjects will be rated on YMRS and the MSC-SADS for any periods suggestive of occurrence of hypomanic symptoms.

2c(ii)A. Human Subjects: The detailed inclusion and exclusion criteria and protection procedures are described in Human Subjects section E1a.

2c(ii)B. Recruitment and Timeline:

1. **Year 1:** Week 1 – 12: Training of study personnel and organization for initiation of study.
2. **Year 1 – Year 5:** Week 12 – Week 234: Recruitment of subjects and conduct of the study.
3. **Year 5:** Week 234 – Week 260: Continued follow-up of subjects and final data analysis and publication.

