2c(ii)F. Antidepressant treatment: SSRIs are the most frequently prescribed antidepressants and are generally well tolerated. We will use SSRI antidepressants or Wellbutrin which are available in generic form i.e. either sertraline, fluoxetine, paroxetine, vilazodone, citalopram, or bupropion. We have elected to use these medications because there is some evidence that they are less likely to induce (hypo)mania. Subjects treatment will be tailored according to clinical needs and the dose adjusted or the medication switched depending on response and side effects. If a patient satisfies criteria for conversion to BD (please see section 2c(ii)G below) at any time during follow-up, the study will be terminated, and either the antidepressant would be withdrawn and the patient treated with a mood stabilizer or continued and a mood stabilizer added upon. Once the patient is stabilized they will be referred to the treater of their choice or to an inpatient facility for appropriate treatment. If at any time point the patient requires other treatment e.g. due to treatment resistance or wants to be treated with psychotherapy only then they will be referred to a treater of their choice but would continue to come for follow-up visits for assessment of mood.

Patients with psychotic symptoms, who can be safely treated as an outpatient, will also be treated with an atypical neuroleptic of their choice per treatment guidelines⁵. The dosage and duration of use of these medication will be recorded, converted to a single standard equivalent and used in the data analysis as detailed in section 2c(ii)la.(adjusting for covariates).

2c(ii)G. Rating Scales:

I. Diagnostic Instruments:

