Questionnaires and Tools	Screening	Basel ine	Wk 2	Wk 4	2 mon	3 mon	Every mon from 4 - 6 months	Every 3 Months from 6 months – 24 Months
Diagnostic Instrument for Genetic Studies	X							
Kiddie Schedule for Affective Disorders and Schizophrenia								
DIGS/KSADS Mood Disorders Section	X							
SCID II	X							
Visual Analog Scale	X							
MINI International Neuropsychiatric Interview (MINI)	X	X	X	X	X	X	X	X
Childhood Events and Life Events Scales	X							
Physical Examination	X							
Clinical Psychiatric Interview	X							
Family Interview for Genetic Studies (FIGS) ⁸²	X							
Laboratory Tests:	X							
fMRI SCAN		X						
Genetic blood draw	X							
S100B , antibody, and cytokine testing	X							
Antidepressant Treatment		X	X	X	X	X	X	X
Hypomania Syndrome Checklist of schedule for Affective Disorders and Schizophrenia (HSC-SADS)	X	X	X	X	X	X	X	X
17-Item Hamilton Depression Scale (HDRS) ⁷⁹ - Children’s Depression Rating Scale (CDRS-R) Hamilton Anxiety Scale (HAM-A) Screen for Child Anxiety Related Disorders (Scared)	X	X	X	X	X	X	X	X
Montgomery-Asberg Depression Scale (MADRS)	X	X	X	X	X	X	X	X
Young Mania Rating Scale (YMRS) ⁷⁷	X	X	X	X	X	X	X	X

Columbia Suicide Severity Rating Scale (CSSRS)	X	X	X	X	X	X	X	X
Beck Scale for Suicide Ideation (BSSI)	X	X	X	X	X	X	X	X
Treatment Emergent Side Effects Scale (TESES)			X	X	X	X	X	X
Clinical Global Impression Scale – for Bipolar Disorder (CGI-BP) ⁸³	X	X	X	X	X	X	X	X

III. Rating for any episodes of subthreshold or over threshold (hypo)manic symptoms: At each follow-up time point the subject will be asked for any sustained periods since the last visit in which they felt more high, irritable or energetic than their normal self³. If the patient answers in the affirmative then they would be rated on the YMRS and MSC-SADS for that period as well as for DSM-IV criteria for conversion to BD.

2c(ii)H. fMRI Scan methodology: Subjects will be imaged using state-of-the-art whole-body 3T Siemens Trio-Tim MRI scanner. Before the imaging session, subjects will be trained regarding experimental procedures. The imaging session duration will be approximately 90 minutes.

Figure 7. Imaging session:

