Specific Aim 1: Differentiation between BDD and UD: We will conduct a one way ANOVA with the connectivity and activation measures as dependent variables to look at differences between groups (BDD and UD). The analyses will be similar to those in our previous studies^{41, 42}. The normality assumptions will be examined using the Kolmogorov-Smirnov test. Box-Cox type transformation methods will be employed if the normality assumption is violated for the outcome variable. To adjust for multiple comparisons accounting for multiple brain ROIs and ad-hoc comparisons conducted within an ANOVA model, Bonferroni adjustment will be used to control overall type I error rates (over-all significance level will be set to 0.05). A post ANOVA logistic regression based classification model will be constructed to build a classifier between BDD and UD. Specificity and sensitivity will be examined using receiver operating characteristics (ROC) curves. We will use leave-one out cross validation method to assess predictive performance of our classification model⁹⁶.

Specific Aim 2: Differentiation between BDD, HRUD, LRUD and healthy control: We will use corticoamygdalar connectivity, amygdalar-LOFC connectivity and ACC Activation in Emotion to perform one-way ANOVA among all four groups. Prior to the analysis, each of these variables will be transformed (using the Box-Cox transformation) so that they will made as close to Gaussian as possible. The normality assumptions will be examined using the Kolmogorov-Smirnov test. Specificity and sensitivity will be examined as in Aim 1.

Specific Aim 3: Identification of imaging measures significantly affecting the rate of conversion from UD to BD: The conversion of UD subjects into BDD is defined as the time to event phenomenon and will be modeled using Cox-proportional hazard model given by,

$$\log(h(t)) = h_0(t) + \beta_1 X_1 + \beta_2 X_2 + \dots + \beta_p X_p$$

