where $h(t)$ is the hazard or rate of conversion at time (t), $h_0(t)$ is the baseline conversion rate and X_i for $i = 1, 2, \dots, p$ are covariates. The subjects will be followed in the fashion described in Table 3 with periodic assessments. The assumption of constant relative hazard rate over time will be tested and remedied if required following data transformation or by incorporating a piecewise constant hazard model. Based on this framework, we will test the significance of imaging and activation measures on the hazard rate. Our primary objective here is to identify those covariates that significantly affecting the hazard rate. The grouping of the UD (HRUD and LRUD) will be also treated as a separate covariate and put in the model as an indicator variable. To detect the progression of disease severity (episodes of (sub) threshold hypo(mania)) we will additionally use Young Mania Rating Scale (YMRS) and the mania syndrome checklist from the Schedule for Depression and Schizophrenia (MSC-SADS) between study visits over during follow-up. We will test the group difference between LRUD and HRUD using mixed-effects linear regression analyses⁹⁷ with repeated measurements taken over two years. Each model will include a random intercept and slope and fixed effects group, and time, as well as the stratification covariates. A likelihood ratio test will examine the incremental contribution of the group effect over time.

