E2b6. Occurrence of hypomania or mania in UD patients during supervised antidepressant treatment phase and during follow-up: the development of subthreshold hypomania or full blown hypomania or mania are the endpoints for this study after which the subject will be terminated from the study and appropriate clinical treatment instituted and after stabilization the subjects will be referred to the treater of their choice. If a patient is deemed to require hospitalization it would be arranged at one of inpatient psychiatric units within the Indiana University School of Medicine. It should be noted that the risk of antidepressant induced mania has been reported only in BD I subjects and there is controversy regarding whether antidepressants can do the same in BD II disorder let alone in HRUD subjects⁷³. In any event, as discussed above, absent a firm diagnosis of BD based on past (hypo)manic symptoms clinically these patients cannot be started on lithium, anticonvulsants or atypical neuroleptics because of concern for side effects and the long-term nature of therapy. Therefore, HRUD subjects either get no treatment and needlessly continue to suffer from depression or more frequently they are treated with antidepressants in a clinical setting (as proposed in this application). However, close monitoring is advisable which the subjects will get in this study and which otherwise they may not get. We have elected to use selective serotonin reuptake inhibitors (SSRIs) or bupropion because there is some evidence that they are less likely to induce (hypo)mania.

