E2b9. Tolerability of fMRI procedures by psychiatric patients: Patients and healthy subjects may become uncomfortable or agitated during the scan. Subjects reporting symptoms of being uncomfortable in closed spaces will not be included in the study. The procedures for fMRI such as stimulus induced activation measurements have been used extensively in our radiology facilities. In the depression study and bipolar patients for which preliminary data has been provided patients tolerated the procedures very well. Other investigators at IUSM have used similar procedures with patients with schizophrenia and substance abuse disorders and the procedures have been well tolerated. The radiology imaging area is well staffed with personnel who have extensive experience in doing fMRI studies. A crash cart and other equipment and medical personnel for medical emergencies are also readily available. Throughout the procedures the patients comfort will be closely monitored and the study will be terminated if needed.

E2b10. Antidepressant treatment: Patients will be monitored and educated in detail for side effects of antidepressants. If a patient develops hypomania or mania they will be terminated from the

study and referred to the treater or their choice or in the worse case to an inpatient unit. The same will be done if the patient develops other unwanted side effects or desire treatment with another antidepressant or modality which cannot be provided in the study.

E2b11. Antipsychotic Treatment: Antipsychotics are generally well tolerated. All subjects will be monitored closely at each visit for any side effects. They will be given emergency phone numbers with which they can contact either the principal investigator or a psychiatrist on the research team who will be available 24 hours, 7 days a week.

E3. Potential benefits to subjects and others:

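### Section E2b6 terminates UD subjects at subthreshold hypomania, below Aim 3's conversion event; followed literally, such subjects are censored before conversion can be seen or miscounted as converters

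*Combined protocol and SAP*

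**What the plan says.** Three places in the combined protocol and SAP say when a UD subject's participation ends for mood reasons.

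- E2b6, which applies in follow-up as well as in the treatment phase: "the development of subthreshold hypomania or full blown hypomania or mania are the endpoints for this study after which the subject will be terminated". Participation ends there, with clinical treatment and later referral.
- 2c(ii)F: "If a patient satisfies criteria for conversion to BD (please see section 2c(ii)G below) at any time during follow-up, the study will be terminated".
- E2b10: "If a patient develops hypomania or mania they will be terminated from the" study. Subthreshold episodes are not named. E2b10 also lists side effects and outside treatment as reasons to stop, which are not at issue here.

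The analysis text separates the two levels. Under Specific Aim 3 in the Statistical Analysis section, "The conversion of UD subjects into BDD is defined as the time to event phenomenon", modelled by Cox regression. Section 2c(ii)G, part III, says how a reported episode is assessed: subjects "they would be rated on the YMRS and MSC-SADS for that period as well as for DSM-IV criteria for conversion to BD". Exploratory Aim 3 makes the lower level an outcome of its own: "Beside conversion to (hypo)mania we will also measure occurrence of episodes of sub-threshold hypomania symptoms". Methods and Design adds that "During the 24 months all subjects will be rated on YMRS and the MSC-SADS for any periods suggestive of occurrence of hypomanic symptoms", and the mixed model comparing LRUD with HRUD is to be fitted "with repeated measurements taken over two years".

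**The concern.** E2b6 puts the exit one step below the event that the Cox model needs. A subject who leaves at a subthreshold episode cannot later be seen to meet DSM-IV criteria. The text does not say how that subject enters the model, and two treatments are open.

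- **Censored at exit.** Exploratory Aim 3 calls (hypo)manic symptoms the main indicator of bipolarity. Exit would then be triggered by the sign thought to mark future converters, and censoring could be informative even among subjects of the same risk group.
- **Counted as an event.** E2b6 calls subthreshold hypomania an endpoint, so an analyst could score it as a conversion. The model would then estimate the hazard of a lower and different event from the one that Aim 3 defines.

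Exploratory Aim 3 says that only prospective data on who develops bipolar disorder can validate the baseline imaging measures. The conversion analysis supplies those data, and it rests on few events.

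**Working it through.** **The plan's own figure.** The sample size section claims 80% power for Aim 3 with 60 per group, conversion of 6% (LRUD) and 14% (HRUD), alpha 0.05 and 20% attrition. It gives no period for the two rates; I take them as cumulative over follow-up.

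- HR = ln(1 − 0.14) / ln(1 − 0.06) = 2.44.
- Schoenfeld power = Φ(√(E/4) × ln HR − 1.96), two-sided.
- E = 60 × 0.20 = 12 events gives 34%; E = 48 × 0.20 = 9.6 events gives 28%.
- Reading the rates as annual over two years gives at most 68% (one-sided, 60 per group).

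The 80% does not reproduce. That is a separate matter, and this point does not depend on it. It does show how few events there are to lose.

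**Expected conversions, E = n per group × (0.14 + 0.06).** Loss rates are from Methods and Design.

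| Loss assumed | n per group | E | One converter as share of E (1/E) |
|---|---|---|---|
| 15% | 60 × 0.85 = 51 | 10.2 | 9.8% |
| 20% | 60 × 0.80 = 48 | 6.72 + 2.88 = 9.6 | 10.4% |
| 10% at baseline, then 20% | 60 × 0.90 × 0.80 = 43.2 | 8.64 | 11.6% |

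**Precision if converters are lost.** For an imaging measure scaled to one SD, SE(log HR) is about 1/√E.

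- E = 9.6: 0.323
- One lost, E = 8.6: 0.341 (about 6% wider)
- Two lost, E = 7.6: 0.363 (about 12% wider)

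The documents do not say how many would be lost, so one and two are illustrations. If 25% or 50% of would-be converters were stopped first (assumed shares), E would be 9.6 × 0.75 = 7.2 or 9.6 × 0.50 = 4.8. These figures concern precision only and say nothing about bias.

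**Background imprecision.** With no such exits, the HRUD/LRUD contrast has SE(log HR) = √(1/6.72 + 1/2.88) = 0.704. The 95% interval is exp(ln 2.44 ± 1.96 × 0.704), about 0.61 to 9.7.

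**The symptom scales.** The episode that triggers exit is itself rated (2c(ii)G, part III), so YMRS and MSC-SADS lose only later peaks and later course. In the mixed model, exit driven by a recorded score is plausibly missing at random. The effect there is milder than in the Cox model.

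**The case against.** The strongest reply is that these subjects are not meant to be lost. E2b7 says UD subjects are followed every three months until the study ends and makes no exception for early stops. Section 2c(ii)E offers phone follow-up to UD subjects who discontinue medication and opt in. The heading of E2b6 names only hypomania and mania, and the section concerns protection against risk, so termination may mean the end of study treatment. This is a plausible account of intent, and it makes the loss of observation conditional. It does not settle the matter: E2b7 deals with referral as the 24 months of treatment end, 2c(ii)E is keyed to stopping medication, and neither names subjects who leave under E2b6, which speaks of leaving the study.

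A second reply concerns risk group. Past subthreshold symptoms can qualify a subject for HRUD and bar entry to LRUD, so a reader might infer that unequal exit biases the comparison. That does not follow. The Cox model includes the HRUD/LRUD grouping as an indicator, and censoring that differs only by a modelled covariate is not in itself a bias. What remains is exit related to conversion risk within a group.

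Third, the planned 15–20% loss may already include some early exits, so subtracting further converters could count them twice. The documents do not say. Fourth, Aim 3 is exploratory and already imprecise. That is correct and limits the stakes.

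**Conclusion.** The conflict is in the current text: E2b6 stops at a lower mood threshold than 2c(ii)F, E2b10 and the Aim 3 analysis. Its consequence is conditional. If E2b6 is followed literally, a subject with a subthreshold episode is either censored before conversion can be observed or miscounted as a converter. With 8.6 to 10.2 expected conversions, each lost converter is about 10% of the events. This rests on reading 6% and 14% as cumulative and on the plan's own loss rates. That conversion means DSM-IV conversion is taken from 2c(ii)G; the Cox paragraph does not repeat it.

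A reader might infer that the hazard ratios will be biased by some amount in a known direction. The documents do not support that: they give no rate of subthreshold episodes and no link from such episodes to conversion in this cohort. Nor are Aims 1 and 2 touched, since they use baseline scans. The point is worth fixing because the remedy is cheap, but its reach is limited to exploratory Aim 3.

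**What to change.** 1. In E2b6, limit termination from the study to DSM-IV conversion, in line with 2c(ii)F and E2b10.
2. At subthreshold hypomania, let the study doctor give whatever clinical response is appropriate, including stopping or changing the antidepressant. E2b6 requires appropriate treatment without specifying it, so no protection is relaxed.
3. For consenting subjects, continue outcome observation to month 24 or conversion, whichever comes first, through study visits or the existing three-monthly phone assessments. Section 2c(ii)E already provides for diagnostic and severity scales by phone, and 2c(ii)D for training in telephone ratings.
4. State in the Aim 3 analysis that DSM-IV conversion is the only Cox event.
5. Record treatment changes after a subthreshold episode, and add a sensitivity analysis that censors at that change.

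The cost is protocol and consent wording and at most eight 30-minute calls (8 × 30 = 240 minutes) per affected subject. Three-monthly calls date a conversion less finely than the monthly visits of the first six months. Some conversions would be observed under changed treatment, which may alter the hazard, since E1b8 notes that antidepressants can precipitate mania. The sensitivity analysis is there for that reason.

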Visit 3 will be one week following visit two and consist of mood questionnaires, Columbia Suicide Severity Rating Scale (CSSRS), Beck Scale for Suicide Ideation (BSSI), TESES (Treatment Emergent Side Effects Scale), and recording of vital signs and weight.

Visits 4 and 5 will be two weeks apart and consist of mood questionnaires, Columbia Suicide Severity Rating Scale (CSSRS), Beck Scale for Suicide Ideation (BSSI), TESES (Treatment Emergent Side Effects Scale), and recording of vital signs and weight.

Visit 6 through 10 will be one month apart and consist of mood questionnaires, Columbia Suicide Severity Rating Scale (CSSRS), Beck Scale for Suicide Ideation (BSSI), TESES (Treatment Emergent Side Effects Scale), and recording of vital signs and weight.

Visit 11 through 16 will be three months apart and consist of mood questionnaires, Columbia Suicide Severity Rating Scale (CSSRS), Beck Scale for Suicide Ideation (BSSI), TESES (Treatment Emergent Side Effects Scale), and recording of vital signs and weight.

BDD, Healthy control subjects, and UD subjects that discontinue medication treatment who opt for follow up (and sign the appropriate consent) will complete the following study procedures:

Phone assessments 1 through 8 will be three months apart and consist of mood questionnaires, and CSSRS/BSSI. These phone calls will take approximately 30 minutes. If subjects report significant mood changes they may be asked to come to the clinic for assessment. Assessment will be done with mood ratings done at V1 and V2.

Genetic Analysis:

A trained phlebotomist will collect the blood sample. Deoxyribonucleic Acid (DNA) is isolated from 10ml of blood using an organic procedure (Madisen et al.1987). The concentration and quality of DNA is determined using absorbance measurements at 260 and 280nm. The serotonin transporter (SLC6A4) proximal 5' regulatory polymorphism will be genotyped by DNA amplification following the protocol of Heils et al. (Heils et al. 1996). The primers stpr5; 5'-GGCGTTGCCGCTCTGAATTGC- 3' and stpr3; 5'-GAGGGACTGAGCTGGACAACCCAC-3' generate 484 and/or 528 base pair products. The amplification reactions are electrophoresed through 3% agarose and visualized by ethidium bromide staining using a UV transilluminator.

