E1b5. Worsening of symptoms: Patients may have worsening of their symptoms during the waiting period before the first scan and during the study. Patients may become severely depressed and grossly disabled or may develop suicidal or homicidal ideation. Patients who become more manic may act impulsively and have poor judgment leading to self harm or harm others.

E1b6. Loss of confidentiality: There may be a loss of confidentiality of information obtained from psychiatric interviews and of the brain imaging data.

E1b7. Tolerability of fMRI procedures by psychiatric patients: Patients and healthy subjects may become uncomfortable or agitated during the scan. The procedures for fMRI and stimulus induced activation measurements have been used extensively in our radiology facilities. In the depression and bipolar study for which preliminary data has been provided patients tolerated the procedures very well. No patients' scan had to be interrupted midway due to patient's mental or physical discomfort. Other investigators at IUSM have used similar procedures with patients with schizophrenia and substance abuse disorders and the procedures have been well tolerated. The radiology imaging area is well staffed with personnel who have extensive experience in doing fMRI studies. A crash cart and other equipment and medical personnel for medical emergencies are also readily available. Throughout the procedures the patients comfort will be closely monitored and the study will be terminated if needed.

E1b8. Antidepressant treatment: Antidepressants are generally well tolerated. Common early side effects are nausea or stomach irritation, jitteriness and increased anxiety, changes in appetite,

constipation, dizziness, dry mouth, headache, increased sweating, taste changes, weight changes, sleep disturbances, sexual dysfunction, and possible increase in suicidal ideation. Antidepressants can also precipitate mania. In line with the purpose of the study, all subjects will be monitored closely every month for the first 6 months and every 3 months thereafter for two years or more frequently as needed and the medication stopped or changed if there are unwanted side effects. In high doses Wellbutrin may cause seizures, subjects with a history of seizures will not be treated with Wellbutrin.

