E2b7. Treatment and Referral after the study: While the BD subjects is being screened and the fMRI scan being arranged and for the UD patients when they are coming to the end of the 24 months supervised treatment, we will start the process of identifying with the patients where they would like to be referred for treatment. A range of treatment options are available in the Indianapolis area including private university and other outpatient clinics and state hospital. We already have a handout available for all the addresses and phone numbers for patient to make an appointment which we routinely give to our research subjects after they finish the study with us. In this study, we will additionally call up the treater of the patient's choice and make sure that subjects will have an appointment. UD subjects will still be followed up every 3 months until the end of the study. As the patients included in this study will present as unmedicated because either they have never been diagnosed before or for some other reason elected not to take medication that was recommended (not an uncommon situation for many young patients) this process will help in patient complying and following through with treatment. In this way we will be able to get patients engaged in treatment which otherwise they are unlikely to get on their own.

E2b8. Loss of confidentiality: Documents which contain patient-identifying data will be kept in locked filing cabinets, with access restricted to authorized investigators participating in the research, and secretarial and administrative personnel who have been informed about the requirement to maintain confidentiality. Computer records that contain patient identifying data will be secured by passwords. Patients will not be identified in any reports or publications that may result from this study. University policies regarding HIPAA regulations for research subjects will be followed.

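### Section E2b10 terminates UD subjects for side effects or for wanting treatment the study cannot give, while other sections keep following them, so exploratory Aim 3 observation can end because of treatment status

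*Combined protocol and SAP*

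**What the plan says.** Several sections describe what happens to a UD subject whose study medication stops or changes.

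- **E2b10 (Antidepressant treatment, under protection against risk).** A patient who develops hypomania or mania is terminated from the study and referred. The next sentence extends this: "The same will be done if the patient develops other unwanted side effects or desire treatment with another antidepressant or modality", where the study cannot provide it.
- **2c(ii)F (Antidepressant treatment).** Dose is adjusted or the drug switched according to response and side effects. A patient who needs other treatment, for example for treatment resistance, or who wants psychotherapy only, is handled differently from E2b10: "they will be referred to a treater of their choice but would continue to come for follow-up visits for assessment of mood".
- **E1b8 (Antidepressant treatment, under potential risks).** Subjects are monitored for two years, with "the medication stopped or changed if there are unwanted side effects". Termination is not mentioned.
- **2c(ii)E (Screening and follow-up).** Eight phone assessments, three months apart and about 30 minutes each, are set out for several groups, including "UD subjects that discontinue medication treatment who opt for follow up (and sign the appropriate consent".
- **2cii (Methods and Design).** "During the 24 months all subjects will be rated on YMRS and the MSC-SADS" for any period suggestive of hypomanic symptoms.
- **E2b7 (Treatment and referral after the study).** "UD subjects will still be followed up every 3 months until the end of the study", said in the context of referral when the 24 months of supervised treatment are ending.

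Aim 3 fits a Cox model for time to conversion and mixed models for repeated YMRS and MSC-SADS scores over two years. Of the Cox model the Statistical Analysis section says: "Our primary objective here is to identify those covariates that significantly affecting the hazard rate". It states no censoring rule and does not say how to treat follow-up that ends because treatment changed.

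**The concern.** The words pointing back in E2b10 can only refer to termination from the study plus referral. A UD subject who leaves for psychotherapy is therefore terminated under E2b10 and kept under observation under 2c(ii)F. A subject with side effects is terminated under E2b10, but under E1b8 and 2c(ii)F simply has the drug stopped, switched or its dose adjusted, and under 2c(ii)E may be phoned every three months. No section says which rule governs.

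If staff follow E2b10, the outcome of Aim 3 is no longer observed, for a reason tied to treatment. Two consequences follow. Conversions after that date go unseen, in an aim with few events. Censoring may also be informative: E1b8 lists jitteriness, increased anxiety and sleep disturbance among common early side effects, and these could overlap with emerging activation. The retrospective question in 2c(ii)G, part III ("At each follow-up time point the subject will be asked for any sustained periods since the last visit"), cannot recover the missing episodes, because it needs a later contact.

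**Working it through.** **1. Rules side by side, before conversion**

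| Situation | E2b10 | Other sections |
|---|---|---|
| Wants psychotherapy only | Terminated, referred | 2c(ii)F: referred, mood visits continue |
| Needs another treatment the study lacks | Terminated, referred | 2c(ii)F: referred, mood visits continue |
| Unwanted side effects | Terminated, referred | 2c(ii)F: dose adjusted or drug switched; E1b8: stopped or changed |
| Stops medication for any reason | Not addressed as such | 2c(ii)E: optional three-monthly calls |

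The first two rows conflict directly. The third is less direct, because the sentence in 2c(ii)F that keeps visits going does not name side effects. Among the rules for treatment change, E2b10 is the only one that ends observation.

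**2. Expected conversions.** Inputs from the sample size section, Specific Aim 3: 14% (HRUD), 6% (LRUD), 60 per group, 20% attrition in both groups (48 left). The period for the rates is not given, so both readings are shown.

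- As 24-month risks: 60 × 0.14 + 60 × 0.06 = 8.4 + 3.6 = 12. After attrition: 48 × 0.14 + 48 × 0.06 = 6.72 + 2.88 = 9.6.
- As annual rates over two years: 1 − 0.86² = 0.2604 and 1 − 0.94² = 0.1164. Then 60 × (0.2604 + 0.1164) = 22.6, and 48 × 0.3768 = 18.1.

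**3. Events lost through termination.** Assumptions, not in the documents: 24-month reading, constant hazard, leavers terminated at month 3, leavers and stayers at equal risk, equal shares leaving in both groups. Month 3 is one eighth of 24 months, so the risk still to come is (1 − p)^(1/8) − (1 − p).

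- HRUD: 0.9813 − 0.86 = 0.1213.
- LRUD: 0.9923 − 0.94 = 0.0523.
- Events after month 3: 60 × (0.1213 + 0.0523) = 10.42.
- Share leaving 5%: 0.05 × 10.42 = 0.52. At 10%: 1.04. At 20%: 2.08.

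These losses are counted from 12. The plan already expects 15–20% of UD subjects to be lost during follow-up and does not say how much of that E2b10 would cause, so the losses may overlap with the step from 12 to 9.6.

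**4. Effect on the HRUD:LRUD hazard ratio.** With everyone followed, the ratio is ln(0.86)/ln(0.94) = 2.44. Let the hazard be L until month 3 and in stayers afterwards, and rL in leavers after month 3, with a share q leaving. Solve for L in each group from

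exp(−3L) × [(1 − q) exp(−21L) + q exp(−21rL)] = 1 − p.

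If leavers are terminated, the Cox model estimates L(HRUD)/L(LRUD). With q = 20% in both groups, the ratio is 2.44, 2.44, 2.45 and 2.47 for r = 0.5, 1, 2 and 3. It barely moves.

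**5. Imaging covariates.** These are the main interest of the Cox model, but the documents give no hazard ratio for them, so no corresponding figure can be calculated.

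**The case against.** The best defence is that the operative follow-up procedures are in 2c(ii)E and 2c(ii)F, whereas E2b10 is a safety paragraph. Those procedures already provide a phone schedule for subjects who stop medication and continued visits for those who go elsewhere. The protocol also uses the word study loosely: in E2b9 it means the scan session. E2b10 might then mean only the end of study treatment, and nothing shows that staff would prefer it to the visit schedule. That limits the point to what can happen if E2b10 is followed. It does not remove it. E2b10 says termination from the study, and applies it in the same way to hypomania and mania, where E2b6 treats termination as the end of participation after an endpoint. The three-monthly promise in E2b7 concerns referral after treatment and does not clearly override E2b10.

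A reader might infer a material bias in Aim 3. The model above can produce ratios from 1.91 to 3.18, but only if leaving is set at 30% in one group and 10% in the other and leavers have three times the stayers' hazard. No document supports those inputs, and the plan's own power statement assumes equal attrition. Even then, with 6.72 and 2.88 events, the standard error of the log ratio is √(1/6.72 + 1/2.88) = 0.70, and the largest shift is ln(3.18/2.44)/0.70, about 0.4 of a standard error.

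A reader might also take 10 to 12 conversions as the plan's stated expectation. That holds only if the rates are 24-month risks. Nor can the whole loss of events be called additional to the plan, given the attrition already allowed for.

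**Conclusion.** The textual conflict is certain: E2b10 terminates subjects whom 2c(ii)F keeps under observation and whom E1b8 and 2c(ii)E do not remove. If E2b10 is followed, Aim 3 loses observation because of treatment status. Aim 3 is labelled exploratory, and Aims 1 and 2 rest on baseline scans, so neither of them is affected.

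The size is modest. On the 24-month reading, with assumed leaving of 5–20% at month 3 and equal risk, about 0.5 to 2 of 12 expected conversions would go unseen, some of them possibly within the budgeted attrition. On the annual reading the expected totals are about 23, or 18 after attrition. Censoring may be informative, but neither the direction nor the size of any bias can be determined from the documents, and equal 20% leaving leaves the HRUD:LRUD ratio at 2.44 to 2.47. A claim that Aim 3 would be materially biased is not supported. What is gained is retained events and one rule for staff to follow. Severity: minor.

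**What to change.** In E2b10, limit termination from the study to hypomania or mania. For side effects, or a wish for treatment the study cannot provide, say that study medication is stopped or changed, the subject is referred as needed, and mood assessments continue to month 24 for subjects who are willing. Those assessments can be the visits already in 2c(ii)F or the three-monthly calls already in 2c(ii)E, each with the look-back question and the YMRS, MSC-SADS and DSM-IV conversion ratings that follow from it.

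The cost is protocol wording plus a few calls per leaver. A subject who stops at month 3 would have seven calls (months 6, 9, 12, 15, 18, 21 and 24), or 7 × 30 minutes = 3.5 hours over 21 months. Training in telephone rating is already planned in 2c(ii)D. Follow-up remains voluntary.

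E2b6 separately terminates subjects at subthreshold hypomania, which also ends observation before conversion. This change does not address that rule.
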